The honest answer is that causes of regional vulnerability are both intriguing and remain elusive. Altering their mechanisms may offer great therapeutic benefits. Yet, rational experiments to alter pathogenic mechanisms can proceed in the absence of knowing how regional vulnerability occurs. In the case of AD and PD, overlapping of clinical phenotypes and pathologies with disease progression implicates similar disease mechanisms, at least in some subjects.

SPECIFIC AIMS

The primary aim of this protocol is to test the safety and tolerability of R-Pramipexole in humans with probable AD. We will also explore changes in oxidative stress and brain metabolic consequences as a "proof of concept" exploratory aim.

Primary Aim: Assess the safety and tolerability of R-Pramipexole in probable AD. Twenty subjects with probable AD will initiate treatment with 100 mg/day of R(+) pramipexole for one month. If tolerated, the subjects will increase to 200 mg/day for one month and then 300 mg/day for the next 4 months. Participants will be contacted by phone every two weeks to determine any adverse events. They will also be examined by a physician, have their vital signs measured and have routine safety blood labs performed every two months.

Exploratory Aim: Assess the effect of R-Pramipexole on oxidative stress and brain metabolic consequences. Prior to initiation of R(+)PPX dosing, we will obtain plasma and spinal fluid for oxidative stress markers and obtain brain glucose metabolism PET scans (2FDG PET). During the last month of 300 mg/day dosing, obtain plasma and spinal fluid samples and repeat 2FDG PET scan.

PRELIMINARY DATA

R(+)pramipexole is a mitochondrially concentrated antioxidant

Pramipexole (PPX) is a benzothiazole synthesized in the 1980's as an apomorphine analogue [27]. The stereospecific synthesis yielded S(-)PPX (Figure 1), which possessed potent and full agonist actions at the D2 family of brain dopamine receptors. S(-)PPX was developed for clinical use in humans and was approved in 1997 by the FDA as Mirapex®, for treatment of Parkinson's disease symptoms due to nigrostriatal dopamine deficiency.

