R(+)PPX slows the progression of disability and decline of respiratory capacity in early ALS subjects (Knopp Phase 2b, Phase 3 pending). The scientific rationale for the current proposed study in probable AD is that oxidative stress is an early abnormality in human AD and transgenic animal models of familial AD. Increased brain oxidative stress is likely causal for AD pathogenesis and can stimulate net production of beta amyloid by increasing beta amyloid synthesis (beta secretase expression) and inhibiting beta amyloid degradation (neprilysin activity). The sponsor's group has shown that mtDNA from AD subjects expressed in a cybrid model can drive increased oxidative stress and beta amyloid production, which is reduced by PPX. The current study will not define how oxidative stress is increased in AD brain, rather it will correct that problem by treatment with a well tolerated and novel mitochondrial antioxidant.

The sponsor has extensive experience testing R(+)PPX in ALS and has an active physician-sponsor IND that has been amended to allow testing of R(+)PPX in AD subjects (see DSMB charter in appendix for more information). Because of conflicts of interest, the sponsor will not be involved at all in recruitment, treatment or evaluation of AD subjects; that will occur at Kansas University Medical Center (KUMC), with [name] as the Principal Investigator. [name],MD, PhD will function as Sponsor in this study but will have no direct involvement in clinical care.

The primary goal of the study is to establish the safety and tolerability of the study medication in individuals with AD. Exploratory variables involve changes in brain and peripheral oxidative stress assayed by isoprostanate levels in spinal fluid and serum, respectively, change in cognitive function and improvement in brain glucose metabolism assayed by FDG-PET scan. The goal of the present study is to establish that up to 300 mg/day of R(+)PPX is tolerated by subjects with probable AD, lowers oxidative stress and may show a trend of improving brain glucose metabolism.

Subject selection and recruitment

Subjects with probable AD will be identified and recruited through the Memory Disorders Clinic at the University of Kansas Medical Center (KUMC). This clinic is under the direction of [name], an accomplished AD clinical investigator.

KU Alzheimer and Memory Program

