Study Drug Administration: R(+)PPX is provided by the sponsor to the KUMC investigational pharmacy as the water soluble dihydrochloride salt, in the form of powder manufactured under GMP conditions by Quality Chemical Laboratories, the supplier of drug for all of [name] studies. The investigational pharmacy prepares a water solution at 10 mg/ml. This solution has been tested by the sponsor and is stable at 4 degrees for at least two months.

Treatment is initiated after the Baseline visit at 100mg a day (50 mg bid in morning and early evening) for 1 month. If tolerated, dosing will increase to 200mg a day (100 mg bid) for a second one-month interval. If at the end of four months of being on study drug, the participant is not experiencing side effects the study drug will be increased to 300mg a day (150 mg bid) where it will remain for the next 4 months. Subjects will be seen every two months for safety assessments prior to any dose escalation and will also be contacted every two weeks by phone (see below). If a participant experiences mild, non-serious adverse events possibly due to the study drug, the study clinician will determine the causality and make a decision whether to continue the study medication and at what dosage. If study drug is discontinued temporarily (>10 days), it will be titrated to the target dose with dose increases no more frequent than once a month.

Drug Accountability: Participants in the study will return any unused drug and study drug containers at each of the safety visits. Study partners will be asked to account for any missed dosages of the study drug and the reason for missing the dosing. Participants are encouraged to maintain 100 percent compliance with dosing. The study partner and the participant will be advised of their

compliance at each safety visit before the study drug is dispensed and means and measures to increase compliance will be initiated. All unused study drug and containers will be returned to the investigational pharmacy for disposal.

Phone Calls: Participants and their study partner will be contacted by the study coordinator every two weeks by phone after starting to take the study medication to review concurrent medications and adverse events.

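### The titration rule in Study Drug Administration runs to week 32, leaves weeks 8 to 16 without a stated dose, and cannot be carried out in the 24-week treatment calendar

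*Combined protocol and SAP*

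**What the plan says.** Three places describe the titration.

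- **Specific Aims, Primary Aim.** Dosing starts at 100 mg/day for one month. Then: "If tolerated, the subjects will increase to 200 mg/day for one month and then 300 mg/day for the next 4 months".
- **Treatment protocol, Study Drug Administration.** The start is the same, followed by: "If tolerated, dosing will increase to 200mg a day (100 mg bid) for a second one-month interval". The last step is conditional and later: "If at the end of four months of being on study drug, the participant is not experiencing side effects", then "the study drug will be increased to 300mg a day (150 mg bid) where it will remain for the next 4 months".
- **Conclusions.** Escalation from 100 to 300 mg/day is described as taking four months.

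The calendar is fixed elsewhere. Safety Visits sets in-person visits every 8 weeks, with drug dispensed at Visits 1, 2 and 3. End-of-Treatment Assessments places the final assessments at week 24 (Visit 4), with remaining drug returned and none dispensed. The safety paragraph of Data analysis counts six months of intervention. The visit schedule closes with an end-of-study visit at week 26.

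**The concern.** Study Drug Administration is the operative text for a site and its pharmacy. If it disagrees with Specific Aims and with the visit calendar, two participants could be treated differently and both be within protocol.

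Exposure at the top dose is what is at stake. Experimental Design and Methods states: "The goal of the present study is to establish that up to 300 mg/day of R(+)PPX is tolerated by subjects with probable AD". Time at 300 mg/day is the evidence for that goal, and the two readings differ twofold on it. The exploratory measures are affected too: the 2-FDG PET subsection and Conclusions both place the second scan after several months at 300 mg/day.

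**Working it through.** **Inputs.** Titration steps come from Specific Aims and Study Drug Administration. Visits on drug fall at weeks 0, 8, 16 and 24 (schedule header, Safety Visits, End-of-Treatment Assessments). Twenty participants are planned (Specific Aims). The protocol describes the same visit interval as two months and as 8 weeks, so one protocol month is 4 weeks (28 days).

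**Reproducing the plan's treatment length.** Specific Aims: 1 + 1 + 4 = 6 months; 6 × 28 = 168 days = week 24. This matches the calendar and the six months of intervention exactly.

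**Study Drug Administration as written.** 4 + 4 = 8 months; 8 × 28 = 224 days = week 32.
- Past the end of treatment: 224 − 168 = 56 days.
- Past the week-26 visit: 224 − 182 = 42 days.
- No stated dose: from the end of month 2 (day 56) to the end of month 4 (day 112) = 56 days, weeks 8 to 16.

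**Exposure by week 24 (day 168).**

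| | Specific Aims | Four-month escalation, stopped at week 24 |
|---|---|---|
| Start of 300 mg/day | day 56 (week 8, Visit 2) | day 112 (week 16, Visit 3) |
| Days at 300 mg/day | 168 − 56 = 112 | 168 − 112 = 56 |
| Planned person-days, 20 participants | 2,240 | 1,120 |
| Cumulative dose per participant | 28×100 + 28×200 + 112×300 = 42,000 mg | 28×100 + 84×200 + 56×300 = 36,400 mg |

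The last cell assumes 200 mg/day is held from week 4 to week 16, which the protocol does not say.

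**Sensitivity to the length of a month.** With calendar months (about 4.35 weeks), Specific Aims ends at week 26.1 and Study Drug Administration at week 34.8. Neither convention makes the latter fit.

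**The week-4 step.** Under every reading, 100 to 200 mg/day falls at week 4, where the calendar has only a phone call. Yet Study Drug Administration says "Subjects will be seen every two months for safety assessments prior to any dose escalation".

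**The case against.** The strongest reply is that four months is a slip for two, and that any site would follow Specific Aims and the calendar. That reading is the best supported, but Conclusions repeats the four-month escalation, so the phrase cannot be dismissed as a lone slip. The documents do not settle what was intended.

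Three stronger readings are tempting and should not be drawn.

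- **A reader might infer that the calendar has to run to week 32.** It does not. Sixteen weeks of escalation plus 8 weeks at 300 mg/day also fits week 24; only the closing four-month period would have to change.
- **A reader might infer that the week-24 scan and lumbar puncture would miss their intended window,** given "During the last month of 300 mg/day dosing, obtain plasma and spinal fluid samples and repeat 2FDG PET scan". That follows only if dosing continues beyond week 24, which the supply rules prevent. With dosing stopped at week 24, weeks 20 to 24 are the last month at that dose. What 8 weeks does strain is the several months at 300 mg/day before the scan.
- **A reader might infer a safety gap, because the 300 mg/day step coincides with a visit whose labs need not be read first.** No text does require those results to be read, and the same holds at Visit 2 or Visit 3, depending on the schedule. But the stated criteria for stepping up are clinical, participants are examined at the visit, and nothing says the new dose starts that day. If it did, and turnaround were 1 to 3 days (an assumption), the exposure would be 2 to 6 doses, each 50 mg higher: 100 to 300 mg in total. Same-day results would make it zero. Preliminary Data reports about 50 people on 300 mg/day for 6 to 9 months, with no drug-related serious adverse events reported across all those treated. Reading the labs first is a reasonable addition; its absence is not an error.

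**Conclusion.** The inconsistency is certain and minor. The rule in Study Drug Administration overruns the treatment period by 8 weeks, omits the dose for 8 weeks, and disagrees with Specific Aims. It leaves planned time at 300 mg/day at either 112 or 56 days, a factor of two on the exposure that supports the study's stated goal. These day counts rest on 4-week months, the protocol's own convention.

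Specific Aims is the best-supported schedule. It fits week 24 exactly, agrees with the six months of intervention, sits better with several months at 300 mg/day before the second scan, and matches the monthly pace set for re-titration after an interruption. That is a judgement on the text, not proof of intent. The finding does not show that participants would be put at risk or that the biomarker assessments would be mistimed.

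**What to change.** State one schedule in Specific Aims, Study Drug Administration and Conclusions.

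- **Preferred:** 100 mg/day in weeks 0–4, 200 mg/day in weeks 4–8, 300 mg/day in weeks 8–24. In Study Drug Administration, change the four months before the last step to two. In Conclusions, change the escalation to about 8 weeks. The cost is wording only.
- **If slower titration was intended, within 24 weeks:** state 200 mg/day through week 16 and 300 mg/day for the 8 weeks after, and amend Specific Aims and the several-months wording. The cost is wording, plus half the time at the target dose.
- **If slower titration and four months at 300 mg/day were both intended:** state 200 mg/day through week 16 and extend visits and dispensing to week 32. The cost is about one more dispensing and safety visit per participant (20 visits), with the final assessments moved.

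Under any option, say how the week-4 phone call satisfies the rule that participants are seen before escalation, or amend that rule.

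Optional: have the study clinician review the safety labs from the visit at which the 300 mg/day step falls, then confirm the step by phone. This is a new procedure of 20 calls. At an assumed turnaround of 1 to 3 days it costs 1/112 to 3/112, or 0.9% to 2.7%, of the time at 300 mg/day on the preferred schedule. No second dispensing should be needed: "The investigational pharmacy prepares a water solution at 10 mg/ml", so the step is a change from 10 ml to 15 ml twice daily.

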Positron Emission Tomography (PET) Scans: Fluoro-deoxy-glucose (FDG) PET imaging will be performed on all participants at baseline and after treatment for 6 months. Participants will be asked to fast for at least four hours prior to the scanning session. The participant's blood glucose will be checked prior to scanning and must be < 180 mg/dL. After the injection of 5 mCi of tracer, subjects will sit in a quiet, dimly lit room for 30 minutes after which they are placed in the scanner. Procedures will be identical to those used extensively by this group in the Alzheimer's Disease Neuroimaging Initiative.

Lumbar Puncture: Participants will arrive in the GCRC in the early morning after an overnight fast for blood and CSF collection. Fasting blood (14 cc) will be drawn for isoprostane analysis. [name] will perform all lumbar punctures. Lidocaine will be used for topical anesthesia and an atraumatic 24 gauge Sprotte needle will be inserted for CSF collection at the L3/4 or L4/5 interspace. 2 cc of fluid will be discarded and 2 cc sent to the local laboratory for routine cell counts, protein, and glucose. Ten milliliters of blood will be collected and spun. The serum sample will be sent to the protocol investigator for isoprostane analyses. After completion of the procedure, participants will be remain in the GCRC; have breakfast; and rest for about 30-45 minutes before being discharged home with post lumbar puncture instructions. A phone call to the participant 24 hours after the lumbar puncture will be performed to assess for any problems following this procedure. The FDG Pet Scan and the lumbar puncture must be completed on two different days at least 24 hours apart.

Safety Visits: Participants will have in-person safety assessments (1.5 hours) in the GCRC every 8 weeks. Vital signs and weight will be measured; concurrent medications and adverse events will be assessed. A physical and neurological examination will be performed by a study clinician. A targeted symptom checklist will be reviewed with the participant and study partner at each visit to assess occurrence of adverse events including those most associated with the use of pramipexole (Mirapex, see table 1 of appendix). Blood and urine will be collected for safety labs. Study drug will be dispensed at safety visits i.e. visits 1, 2, and 3. Cognitive testing (ADAS-Cog) will be administered at each safety visit.

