End-of-Treatment Assessments (Visit 5): Final outcome assessments will be completed during week 24 visit/ Visit 4 and consist of identical procedures to the baseline assessments (see above): 1) Cognitive testing at the KU Alzheimer and Memory Program (1 hour), 2) FDG PET scanning in the radiology department (1.5 hours), and 3) GCRC visit for a blood draw and lumbar puncture (2 hours). In addition the participant will have a physical/ neurological examination, safety laboratory sampling, vital signs, concurrent medications and adverse events. The participant will return all remaining study drug and containers at this visit. No additional medication will be dispensed.

End-of-Study Visit: Participants will return two weeks after completing the R(+)PPX treatment for a final physical and neurological exam and review of adverse events.

Data analysis

Primary Aim: Safety

Subject safety is the primary variable and item of greatest concern in this study. The extensive dosing experience with R(+)PPX in ALS subjects, many of whom have mild dementia, combined with its lack of detectable D2 dopamine receptor activity *in vivo* at 300 mg/day dosing, support its safety in probable AD subjects. Safety and tolerability will be evaluated by frequent contact with subjects and caregivers and lab safety studies every two months. The frequency and severity of adverse events will be examined and their potential causal relationship to the study drug (as determined by the study physician) will be assessed (the adverse events related to Mirapex [pramipexole] are listed in table 1 of appendix). This information will be used to guide dose selection and inform a more definitive safety and efficacy study. Additionally, cognitive performance data will be acquired every two months to assess the cognitive trajectory to explore possible dose-related changes in cognitive decline over the 6 months of intervention.

Exploratory Aims

Oxidative stress

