The sponsor studied S(-) and R(+) PPX in his laboratory beginning in 1997 and has clinically tested R(+) pramipexole in ALS subjects under a physician-sponsor IND since 2004. R(+)PPX is now commercially licensed and under separate development for treating ALS by Knopp Neurosciences. R(+)PPX is a brain and mitochondrially concentrated antioxidant that can be safely administered to humans at daily doses up to 300 mg/day and has no detectable DA receptor activity *in vivo*. At this dose many subjects achieved trough steady-state PPX levels of >1 μ M, predicting brain levels of >6 μ M that are clearly in the ROS scavenging and neuroprotective levels. R(+)PPX at 300 mg/day substantially improves the course of ALS in short-term studies and will enter Phase 3 testing later this year.

The present application seeks to introduce R(+)PPX treatment to subjects with early AD. In this protocol the subjects will undergo careful dose escalation from 100 mg/day to 300 mg/day R(+)PPX over 4 months. Subjects will have regular serum, combined with baseline and late treatment spinal fluid samples, assayed for isoprostanes as measures of oxidative stress. Serum and spinal fluid will also be assayed for [PPX]. As a measure of cerebral metabolism, brain 2-FDG PET scans will be obtained at baseline and after several months of dosing with 300 mg/day R(+)PPX.

The goal of the present study is to determine if R(+)PPX can be administered in high doses to probable AD subjects, and if so, whether oxidative stress is reduced and cerebral metabolism is increased. Hopefully the results from this study will justify the cost of a larger early efficacy study in probable AD.

Data Management

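### The protocol promises an in-person safety assessment before any dose escalation, but the first doubling (100 to 200 mg/day) falls at one month, about four weeks before the first on-drug visit

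*Combined protocol and SAP*

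**What the plan says.** The assurance is in Treatment protocol, Study Drug Administration: "Subjects will be seen every two months for safety assessments prior to any dose escalation".

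The time of the first step is given twice, and the two places agree. The Primary Aim under Specific Aims starts participants on 100 mg/day for one month and continues: "If tolerated, the subjects will increase to 200 mg/day for one month and then 300 mg/day for the next 4 months". Study Drug Administration also gives 100 mg/day for one month, then: "If tolerated, dosing will increase to 200mg a day (100 mg bid) for a second one-month interval".

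The contacts are described separately. Safety Visits says: "Participants will have in-person safety assessments (1.5 hours) in the GCRC every 8 weeks". These visits include vital signs, a clinician's examination and safety laboratory tests. They also include the symptom list: "A targeted symptom checklist will be reviewed with the participant and study partner at each visit". Under Phone Calls, participants and their partners are "contacted by the study coordinator every two weeks by phone after starting to take the study medication to review concurrent medications and adverse events". The visit-name row of the Schedule of Study Procedures and Assessments has Visit 1 at week 0, calls at weeks 2, 4 and 6, and Visit 2 at week 8.

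The Conclusions section describes the titration differently: "careful dose escalation from 100 mg/day to 300 mg/day R(+)PPX over 4 months".

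**The concern.** The assurance covers every escalation, and the calendar cannot deliver it at the first one. A site can keep the one-month step or the prior in-person assessment, but not both.

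Safety and tolerability is the primary aim. Of the safety data, the Data analysis section says: "This information will be used to guide dose selection and inform a more definitive safety and efficacy study". If the first on-drug examination and laboratory tests come after participants have moved to 200 mg/day, the study has no such data at 100 mg/day for anyone who escalated on time. A laboratory, vital-sign or examination abnormality first seen at week 8 could have arisen on either dose. The same section hopes to explore dose-related cognitive change, yet the first on-drug ADAS-Cog is also at week 8, when these participants are already on 200 mg/day.

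**Working it through.** The question is one of timing, so the check sets the dose steps against the contact calendar. The plan gives no figure of its own to reproduce.

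**Inputs**
- First step: one month after starting (Primary Aim; Study Drug Administration).
- Second step: after a further month (Primary Aim), or at the end of four months on drug (Study Drug Administration).
- Time at 300 mg/day: four months in both places.
- In-person visits: weeks 0, 8, 16 and 24. Calls before the first on-drug visit: weeks 2, 4 and 6 (Schedule).
- Assumption: one month is 4.0 to 4.35 weeks.

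**First step against first on-drug visit**
- Step at week 4.0 to 4.35; visit at week 8.
- Gap: 8 − 4.35 = 3.65 weeks to 8 − 4.0 = 4.0 weeks. The step comes first at either end of the range.
- Visit 1 at week 0 is in person, but it is the first dispensing and gives no on-drug information.
- Scheduled on-drug contacts by the step: the calls at weeks 2 and 4.
- Drug is dispensed only at Visits 1, 2 and 3, so week 4 has no dispensing contact either.

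**Second step against visits**
- Primary Aim: 2 months, about week 8, at Visit 2.
- Study Drug Administration: 4 months, about week 16, at Visit 3.
- The assurance holds for 300 mg/day on either text.

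**On-drug in-person assessments by dose, per on-schedule participant** (4-week months; a visit on the day of a step is counted under the dose just completed)

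| Timetable | 100 mg | 200 mg | 300 mg |
|---|---|---|---|
| Primary Aim (steps at weeks 4, 8) | 0 | 1 (wk 8) | 2 (wk 16, 24) |
| Study Drug Administration (steps at weeks 4, 16) | 0 | 2 (wk 8, 16) | 1 (wk 24) |
| Steps at weeks 8, 16 | 1 (wk 8) | 1 (wk 16) | 1 (wk 24) |

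The second row assumes that 200 mg/day continues to week 16 and treatment ends at week 24. The protocol gives no dose for months 3 and 4 on that wording.

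**Could two-month steps be what was meant?** The four-month titration in Conclusions fits steps at weeks 8 and 16, which would restore the safeguard. It contradicts the one-month interval stated in both dosing passages. Four months at 300 mg/day would then end at 16 + 16 = week 32, which is 32 − 24 = 8 weeks past the scheduled end of treatment. The Primary Aim's timetable does fit: 1 + 1 + 4 = 6 months. Study Drug Administration also allows re-titration increases as often as monthly, so the one-month interval is not an obvious slip.

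**The case against.** The strongest reply is that this is one drafting error seen from another side. The protocol already disagrees with itself about when 300 mg/day starts. If the sponsor confirms two-month steps, Visits 2 and 3 precede both escalations and the problem goes. If the Primary Aim governs, it describes a coherent design of monthly steps, fortnightly calls and two-monthly examinations, and only one clause in Study Drug Administration promises too much. The link is real and the two points should be settled together. Either resolution still needs a text change: to the one-month interval in two places, or to the assurance.

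A second reply is that the coordinator is not said to clear the dose. That is correct: no one is named to judge tolerability at one month. The study clinician decides on dosage when a mild event possibly due to the drug occurs, and all adverse events go to the investigator and sponsor. Even so, before the first step any such decision would rest on what the calls bring in, because no other on-drug contact is scheduled.

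A third reply is that dose attribution is weak anyway. In a single-arm, 20-subject titration, dose is confounded with time on drug, and no laboratory analysis by dose is planned. This stands as a limit. A visit at 100 mg/day would show the dose at detection, not prove causation.

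**Conclusion.** The conflict holds. For participants who escalate on schedule, the promised in-person assessment is not delivered before the first doubling, which precedes the first on-drug visit by about 3.65 to 4 weeks. They have no in-person assessment at 100 mg/day on either dosing text. This rests on the one-month interval, the 8-week visits and the schedule's entries for weeks 0 to 8. The unclear alignment of some schedule rows after week 8 plays no part.

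The consequence is limited. Symptomatic events can be dated from the fortnightly calls. Participants held at 100 mg/day would be examined on that dose at week 8. The rules for removing a participant with a grade 3 event and for stopping the study apply throughout, and the step to the highest dose follows a visit. It should be corrected, but it does not undermine the study.

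**What to change.** Settle this together with the start of 300 mg/day. Which timetable is right is for the sponsor.

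- **If the one-month step is kept:** limit the in-person assurance to the 300 mg/day step. Require the study clinician to review the week-4 call, covering adverse events and the targeted symptom checklist, before clearing 200 mg/day. State in the report that participants who escalated on schedule have no on-drug examination, vital-sign or laboratory data at 100 mg/day. The cost is a wording amendment and one call review per participant, with a weaker safeguard than the one now stated.
- **If the assurance is kept:** tie the steps to the existing visits at weeks 8 and 16 and correct the one-month interval in both dosing passages. No visit is added, but time at 300 mg/day falls from 24 − 8 = 16 weeks to 24 − 16 = 8 weeks, or treatment runs about 8 weeks longer. Eight weeks also sits poorly with the plan to repeat the PET scan after several months at that dose.

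An added week-4 visit with examination, vital signs and laboratory tests would keep both the monthly step and the assurance. It costs one extra visit per participant, up to 20 in all.
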